- (4) Does hormonal contraceptive use affect nutritional status for women with low body mass index?

- (5) What is the percent agreement between CF Clinic DXA scan T-scores and CFFPR data about osteoporosis, osteopenia and bone fracture?
- (6) Are women who use CFTR modulators and more likely to become pregnant unintentionally while taking hormonal contraception (compared to women on non-hormonal contraception)?
- (7) Does use of hormonal contraception result in a higher proportion of patients with mucoid vs. non-mucoid *Pseudomonas aeruginosa* compared to non-hormonal contraceptive users?

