3.0. Hypothesis

- Estrogen-containing methods, but not progestin-only methods, reduce the annual rate of pulmonary exacerbations, the microorganisms associated with a more rapid decline in lung function, and improve ppFEV1 (or absolute FEV1) of women with CF when compared to women with CF who use non-hormonal contraception (control group).
- Estrogen-containing oral methods of birth control are associated with higher incidence of gallbladder disease (defined as gallstones, requiring surgery), increased liver function enzyme values, and/or increased incidence of thromboembolism among women with CF.
- Both estrogen-containing and progestin-only hormonal methods improve BMI among women with CF, which is linked to nutritional status.
- The strength of agreement between DXA scan T-scores and CFFPR data about osteoporosis, osteopenia and bone fracture will be "substantial."
- The effectiveness of oral birth control is reduced compared to other methods of hormonal birth control in the presence of CFTR modulator use.
- Hormonal birth control use results in a greater proportion of patients with mucoid *Pseudomonas aeruginosa*, in patients who are *P. aeruginosa* positive, compared to non-hormonal contraceptive users.

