4.2. Secondary Study Objectives/Endpoints

- To assess the association of hormonal contraceptive use on trends in lung function (FEV1) over time, compared to non-hormonal contraceptive users (primary control) and non-contraceptive users (secondary control).
- To assess the association of hormonal contraceptive use on the incidence of venous or arterial thromboembolism.
- To assess the association of hormonal contraceptive use on prevalence of liver dysfunction, defined as gallstones (requiring surgery), hepatic steatosis, hepatic cirrhosis, and/or incidence of increased liver enzyme test values (ALT/GGT). Increased liver enzymes is defined as exceeding upper limit of normal on at least 3 occasions over 12-month period.
- To assess the association of hormonal contraceptive use on serum glucose trends, incidence of insulin resistance or time to CF-related diabetes (requiring insulin treatment).

- To assess association of hormonal contraceptive use on nutritional status through the evaluation of BMI trends.
- To validate bone health information in CFFPR with chart data obtained from one CF center (limited due to need for data use agreements between institutions for EMR data).
- To determine if those using hormonal contraception while using CFTR modulators report higher rates of unintended pregnancy compared to those taking non-hormonal contraception.
- To assess proportion of mucoid *P. aeruginosa*, in patients who are *P. aeruginosa* positive, among hormonal contraception users compared to non-hormonal contraceptive users.

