7.5. Outcomes (include DAG diagrams to show relationships between exposure and outcomes)

Table 5: Outcomes and associated confounders and covariates

Exposure of interest	Outcome	Confounders/Covariates	Rationale
Combined	Pulmonary outcomes	Smoking	Affects lung function
hormonal contraception (CHC)	 Annual pulmonary exacerbation rate (PEx) (defined as episodes requiring intravenous 	Insurance status (reflection of SES)	Will be used as socioeconomic indicator. Less access to meds may mean less
&	antibiotic use at home or in		compliance
Progestin-only	hospital)Absolute change in FEV1 (in	Age	Lung function worsens as one ages
contraception	liters) Prevalence of micro-organism (defined as 1 or greater sputum	Education (reflection of SES)	Affects contraceptive knowledge decision making
	culture within a 12-month period)P. aeruginosa	ВМІ	Associated with better or worse health status in general

Exposure of interest	Outcome	Confounders/Covariates	Rationale
	 MDR P. aeruginosa Staph aureus 	Exercise	May reduce pulmonary exacerbation rates
	MSSA MRSA	CF genotype class	Associated with severity of disease
	Secondary infections: • Burkholderia cepacia	CFTR modulator treatment	Likely preserves pulmonary decline
	 Burkholderia cenocepacia Mycobacterial species –includes M. tuberculosis and NTM species 	Comorbidity with CFRD (defined as requiring chronic insulin therapy) (11)	Associated with worse disease (reduced immunity)
		Length of hormonal contraceptive use (person-year of exposure)	
	Venous/arterial thromboembolism (VTE)	BMI ≥ 30	
	 Noted on self-respondent survey (defined as blood clot requiring anticoagulation treatment) 	Age > 35 years PMHx for thrombophilia Arterial/venous lines or ports Pmhx cancer Smoking	
	Liver outcomes	BMI	Obesity contributes to
	 Liver disease, non-cirrhosis Gallstone, requiring surgery/procedure (defined as present or absent as 	Comorbidity with diabetes	liver dysfunction Associated with worse disease (reduced immunity)
	recorded in CFFPR)	Hepatitis	Risk factor for liver dysfunction
		CF genotype class Length of hormonal contraceptive use (person-year of exposure)	
	 Serum ALT, GGT (meets criteria if hepatic transaminases and GGT levels exceed upper limit of normal on at least 3 consecutive occasions over 12-month period) (12) 		Will track meeting criteria annually over time
	CF-related diabetes		
	 Serum ogtt trends New onset insulin resistance or diabetes (defined as 		

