9.3. Statistical Methods

Because this is a retrospective cohort study, we are most interested in determining whether this exposure (to hormonal contraception) is associated with our primary outcome (counting the number of pulmonary exacerbations requiring additional IV in a given year) and/or our secondary outcomes (new respiratory microbiology, liver disease/non-cirrhosis, gallstone, requiring surgery/procedure, improved BMI, incidence of VTE, osteoporosis and fragile bone fracture). Women on hormonal contraception will be compared to the primary control group of women on non-hormonal contraception. We will also compare to women on no contraception, as the secondary control group. We will exclude persons with these existing diagnosis at the start of the follow up period for outcome data (January 1, 2010). Within this objective we will be able to calculate incidence rates, relative risks and confidence intervals. We will use Poisson regression to calculate progestin-only and combined hormonal method to non-hormonal method pulmonary exacerbation rate ratios and 95% confidence intervals. This allows for adjustment of follow-up time of each individual.

(Objective 1a): We will evaluate lab values over time (ppFEV1%, serum AST, ALT, alkaline phosphatase) to determine if trends between hormonal contraceptive users and non-hormonal contraceptive users differ. See Table 5 for confounders and covariates that we will use to adjust for the primary and secondary outcomes.

We will model ppFEV1 via generalized estimating equations (GEE), allowing for correlation within a subject, and compare via a fixed effect for exposure. Among women who change or stop contraception, we will estimate and compare within-participant difference in outcomes via the model (if numbers allow). We will censor women who switch method types or become pregnant, and for 6 months post pregnancy, for the primary analysis and subsequently follow them to leverage within-patient data and analyze changes in pulmonary status and contraception. Presence of respiratory microbiology will be estimated longitudinally via GEE with a logit link function. Graphic displays and summary statistics will be used; all *p* values will be two-sided.

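### The mucoid share is taken only among P. aeruginosa-positive women, although positivity is itself an outcome of the exposure, so the share alone cannot support a causal statement about mucoid disease

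*Combined protocol and SAP*

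**What the plan says.** The restriction to positive women appears in two places. The last objective in section 4.2 assesses the mucoid proportion "in patients who are *P. aeruginosa* positive, among hormonal contraception users compared to non-hormonal contraceptive users". The last hypothesis in section 3.0 reads "Hormonal birth control use results in a greater proportion of patients with mucoid *Pseudomonas aeruginosa*, in patients who are *P. aeruginosa* positive". Research question 7 in section 2.0 has the same structure, asking about a "higher proportion of patients with mucoid vs. non-mucoid *Pseudomonas aeruginosa* compared to non-hormonal contraceptive users". No section gives mucoid infection over all women as an endpoint.

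The plan also treats positivity as something the exposure may change. Among the pulmonary outcomes of combined and progestin-only contraception, Table 5 (section 7.5) lists "Prevalence of micro-organism (defined as 1 or greater sputum" culture in a 12-month period, and P. aeruginosa heads the list of organisms. The first hypothesis in section 3.0 expects estrogen-containing methods, but not progestin-only methods, to reduce "the microorganisms associated with a more rapid decline in lung function". Section 9.3 counts new respiratory microbiology among the secondary outcomes.

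For the analysis, section 9.3 says only: "Presence of respiratory microbiology will be estimated longitudinally via GEE with a logit link function". It gives no separate model, denominator or timing rule for the mucoid comparison, and Table 5 does not list mucoid status. Section 9.3 excludes existing diagnoses at January 1, 2010, but does not say whether that covers organisms.

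**The concern.** The denominator of the mucoid share is a group whose membership may depend on the exposure. Women who are positive while using a hormonal method need not be comparable with women who are positive while using a non-hormonal one, and the share can move because its denominator moved.

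The error can run in either direction. If a method prevents or clears non-mucoid infection and leaves mucoid infection alone, the mucoid share rises with no added mucoid disease, and the result looks like the harm named in section 3.0. If a method increases non-mucoid infection, a real mucoid excess can be diluted out of sight. The study is meant to inform advice on contraceptive safety in CF, and the mucoid hypothesis is stated as an effect of hormonal use, so a share that could be read either way is a weak basis for it.

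**Working it through.** **No planned figure to reproduce.** The documents give no P. aeruginosa prevalence, mucoid rate, sample size or power for this comparison. Table 8 concerns the exacerbation rate ratio and does not bear on it. Every prevalence below is an assumption.

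**Inputs**
- Control group: 50% of women P. aeruginosa-positive and 30% mucoid, so 20% non-mucoid (assumed).
- Hormonal group: mucoid 30% of all women, as in controls; non-mucoid lower by a fraction f (assumed 10%, 30% or 50%).
- Group size N: 150 or 250 (assumed). Section 7.7 expects about 600 women, about half on hormonal methods. The remainder must supply both the non-hormonal users and, per section 8.1, the women who never used contraception.
- Alpha 0.05 (section 7.7), two-sided (section 9.3).

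**Step 1: the share.** Share = mucoid / (mucoid + non-mucoid).
- Controls: 0.30/0.50 = 60.0%
- f = 10%: 0.30/(0.30 + 0.18) = 62.5%
- f = 30%: 0.30/(0.30 + 0.14) = 68.2%
- f = 50%: 0.30/(0.30 + 0.10) = 75.0%, an odds ratio of (30/10)/(30/20) = 2.0

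Over all women, mucoid prevalence is 30% against 30% throughout.

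**Step 2: chance of a significant difference.** With p0 and p1 the shares, n0 = 0.50N positives in controls and n1 = (0.30 + non-mucoid) × N in hormonal users:

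z = (p1 − p0) / √[p0(1 − p0)/n0 + p1(1 − p1)/n1], and chance = Φ(z − 1.96) + Φ(−z − 1.96).

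For f = 50% and N = 150: n0 = 75, n1 = 60, standard error = √(0.24/75 + 0.1875/60) = 0.0795, z = 0.15/0.0795 = 1.89, chance 47%.

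| Fall in non-mucoid | Share, hormonal vs control | N = 150 | N = 250 |
|---|---|---|---|
| 10% | 62.5% vs 60.0% | 6% | 7% |
| 30% | 68.2% vs 60.0% | 17% | 26% |
| 50% | 75.0% vs 60.0% | 47% | 68% |

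This treats each woman as one independent observation; the longitudinal model would give somewhat different figures.

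**Step 3: other assumed prevalences.** With positive/mucoid at 60%/30% or 40%/20%, the control share is 50.0% and the three falls give 52.6%, 58.8% and 66.7%. With 70%/45% it is 64.3%, going to 66.7%, 72.0% and 78.3%. The shift is of similar size in each setting.

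**Step 4: boundary cases**
- Equal proportional effect on both forms, for example both down 30%: 0.21/0.35 = 60.0%. No distortion.
- Both forms fall, non-mucoid by more (mucoid 27%, non-mucoid 12%): 0.27/0.39 = 69.2%. The share rises although mucoid disease falls.
- Both forms rise, non-mucoid by more (mucoid 33%, non-mucoid 26%): 0.33/0.59 = 55.9%. The share falls although mucoid disease rises.

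**The case against.** **The conditional question looks deliberate.** The research question, hypothesis and objective all concern phenotype given infection, and the objective in section 4.2 asks only to assess a proportion. This stands: the share is a legitimate description. It supports adding an estimate, not removing the endpoint. What the share cannot do is bear the causal verb in section 3.0.

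**Positivity is analyzed in its own right.** Table 5 and the logit GEE would show a protective effect on P. aeruginosa, and positivity multiplied by share recovers mucoid prevalence. This stands in part. A careful reader could combine the two results if they covered the same women, the same year and the same adjustment, but the plan does not commit to that and Table 5 omits mucoid status.

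**The 50% fall is extreme.** It stands that 47% and 68% belong to the largest effect assumed here. If a 50% fall applied only to estrogen users, and they were half of hormonal users (assumption), the pooled fall would be 25%. The share would be 0.30/0.45 = 66.7% and the chance of significance about 13% or 19%. At a 10% fall it is close to the nominal 5%.

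**A reader might infer that the plan's own hypothesis predicts the distortion.** The documents do not support that. The organism hypothesis covers estrogen-containing methods only, does not name P. aeruginosa and does not separate mucoid from non-mucoid, whereas the mucoid comparison pools all hormonal users. Nowhere does the plan hypothesize the differential effect that the distortion needs.

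**Nor do the documents prove that positivity is determined after exposure.** They do not say when it is determined. That is a gap to close, and until it is closed nothing rules out selection after exposure.

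**Conclusion.** The point holds as a limit on interpretation. The mucoid comparison conditions on a status that Table 5 treats as an outcome of the same exposure and that is not fixed beforehand, so the share can change without a matching change in mucoid disease, in either direction.

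The distortion requires contraception to act differently on non-mucoid and mucoid infection. Under the assumed prevalences it ranges from negligible (2.5 percentage points at a 10% fall) to substantial (15 points at a 50% fall). It would be too strong to say that a benefit will be reported as harm: that depends on a differential effect of unknown size and on the share being read by itself. This is a secondary objective and the correction is cheap, so the plan should make it.

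**What to change.** In sections 4.2 and 9.3:

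1. Add mucoid P. aeruginosa prevalence among all women cultured in the year, by method type (estrogen-containing, progestin-only, non-hormonal), with non-mucoid prevalence beside it. Use the logit GEE already planned. Base any causal statement on this estimate, subject to the usual limits of an observational comparison.
2. Keep the mucoid share among positives as a descriptive result, and reword the section 3.0 hypothesis to match.
3. State when P. aeruginosa status is determined relative to method use, and whether the January 1, 2010 exclusion in section 9.3 applies to organisms. Report how many women were not cultured or had unknown mucoid status.
4. As a supporting analysis only, report conversion to mucoid among women known to be positive and non-mucoid at method start. This is limited to women with a baseline culture, hence method start in 2010 or later, because exposure is asked from 2008 (section 9.1) while the requested registry data begin in 2010 (Appendix).

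Cost: items 1 to 3 need wording and slightly more analysis, since the Appendix already requests the encounter-level fields for culture done, P. aeruginosa found, mucoid, non-mucoid and unknown status. Item 4 will rest on a smaller sample, and some women may give only their age at first and last use of a method (Table 10), which blurs its start date.

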5.0. Trial Design

This is a non-randomized, non-interventional, observational cohort design among reproductive-aged women (ages 18-45 years) with CF. This protocol describes a pilot phase, as well as a larger retrospective approach.

We intend to ask about 625 female participants to provide information about their types of past contraceptive use from 2008 through the most recent data available from CFFPR (2018 or 2019). Before initiating our trial among up to 625 respondents, we intend to pre-test the survey questions on our self-respondent questionnaire among as many as 50 women with and without CF through CFF Community Voice, the Cystic Fibrosis Research, Inc. (CFRI), and the Cystic Fibrosis Reproductive and Sexual Health Collaborative (CFReSHC). Pre-testing our survey questions will help ensure contraceptive, pregnancy, and other reproductive health data from respondents for the larger phase of this study are as complete and accurate as possible.

Once the survey has been piloted and revised accordingly, we will collect past contraceptive, pregnancy and other reproductive health data from up to 625 women at 10 different CF centers. We may over-sample by 25 participants because it is possible that some participants from UW, UTSW and National Jewish may have participated in our earlier published study related to contraceptive use and CFFPR (4). Recruiting through the CF centers will help ensure that women with a confirmed diagnosis of CF respond to the finalized survey. We will link respondent self-reported contraceptive and reproductive health data with CFFPR clinical data. We will ask for EMR data from the 10 different CF centers to validate DXA scan results with findings regarding osteoporosis, osteopenia, and bone fracture in the CFFPR. We plan to randomly select about 10 consented subjects from each of the centers for the EMR DXA scan chart review. Because of our need to link questionnaires and clinical case report forms correctly to the same women with CF in the CFFPR clinical data, we need to request identifiable information, including the CFFPR member ID number.

6.0. Pilot Survey Phase

Given the critical nature of collecting exposure (contraceptive) data for this retrospective approach, the UW study proposed using part of the first year of this grant to pre-test the self-respondent questions with up to 50 women with and without CF. The purpose of this pilot survey is to determine the best approach to collection reproductive health information due to the sensitive nature of question on the topics of contraceptive use, pregnancy and menstruation.

Because this phase may affect how we collect the data in the larger phase of this work, we will simultaneously be refining our analysis plan as we collect, summarize, and analyze our findings during this pre-test/pilot phase.

6.1. Pilot Recruitment

We intend to recruit up to 50 participants through the CFF Community Voice program, CFRI, and CFReSHC. We intend to enroll women between the ages 18-45 years with or without CF. We have chosen the CFF Community Voice program because participants have already agreed to participate in research and we believe they will be forthcoming about their thoughts about the understandability and format of our questions seeking to gather information about past contraceptive use. Inclusion/Exclusion criteria for the pilot phase are listed below:

Table 1: Pilot phase inclusion and exclusion criteria

Pilot inclusion criteria
Female
Aged between 18-45 years.
Functional email address
Has device capable of using Zoom
Pilot exclusion criteria
Receives CF care at one of the 10 collaborating CF centers

6.2. Pilot Process: Please see Pilot Pre-test Survey Protocol for Details

We will not be able to validate responses against the EMR because of research suggesting that EMR data are not accurate with regards to contraceptive information (9).

6.3. Pilot Duration

This phase is expected to take up to 5 months, depending on the number of interviewees needed for question pretesting. During this phase, the research coordinator (RC) will schedule and enroll participants, pre-test the questions, and implement feedback. We will be working closely with the Washington State University (WSU) Social and Economic Sciences Research Center who will provide survey development guidance, as well as the UW Social Development Research Group (SDRG) who will provide expertise on cognitive interviewing.

7.0. Methods: Participants, Interventions, and Outcomes of Final Questionnaire Phase

Once the questionnaire is pretested (anticipated end date of pre-testing is July 2020), the final questionnaire will be revised accordingly prior to initiating the full, larger study.

7.1. Study Setting

We intend to enroll up to 625 women, aged 18-45 years, at 10 separate CF centers. We may over-enroll the sample by 25 women to account for women who may have participated in the prior contraceptive study in 2017. This will allow us to perform a sensitivity analysis excluding women who participated in the pre-study, while maintaining study power.

Name of Institution	Institution PI(s)	Number of women with CF aged 18-45 years
University of Washington	[name], MPH	141
	[name]	
University of Texas Southwestern	[name], MS	140
National Jewish Hospital	[name], MS	233
University of California San Diego	[name]	120
	[name], MPH	
University of Pittsburgh	[name], MS	106
University of Pennsylvania	[name]	128
	[name], MPH	
John's Hopkins University	[name], MPH	159
University of Alabama	[name]	135
	[name]	
	[name] RN	

Name of Institution	Institution PI(s)	Number of women with	
		CF aged 18-45 years	
Harvard U/Boston	[name]	189	
Mount Sinai	[name]	51	

We anticipate that each site will be able to enroll 50% of eligible women ages 18-45 years into the study. We have chosen the lower age range because of estimated age of sexual debut among young women with CF is between ages 16-17 years (5) and it is expected that some women aged 18 will have started using contraception. We have chosen the upper age range of 45 years because of the lower life expectancy of women with CF compared to the general population and inherent bias that adults with CF who live past the currently life expectancy are most likely healthier than younger adults with CF (10).

Table 3: Age distribution goals for study enrollment

Age Distribution of Women with CF		
Age Range (years)	Approximate number of subjects planned	
18-35	383	
36-45	192	

7.1.1. Study Duration

Participant enrollment will take approximately 15 months for the finalized survey phase.

